7.2 Start of the trial

The trial is considered started upon the first act of recruitment of a potential subject. For this trial this is considered as the first patient being informed about the study by his/her treating physician.

The start of the trial shall be notified to the RA within 15 calendar days.

The first visit of the first subject (i.e. when the first subject or his/her legally designated representative signs his/her first informed consent to participate in the trial) (FVFS) will also be notified to the RA within 15 calendar days.

7.3 End of the trial

7.3.1 For an individual subject

The subject has completed the trial when he or she has completed all phases of the study, including the last visit or the last scheduled procedures, as described in this protocol.

7.3.2 For the whole trial

The end of the recruitment of subjects shall be notified to the RA within 15 calendar days. Overall, the end of the trial is reached 30 days after the last study procedure for the last subject has occurred (the last visit of the last subject, LVLS).

As soon as the whole trial has ended (cfr. the definition above), the RA shall be notified within 15 calendar days.

A summary of the results of the trial will be submitted to the RA within 1 year from the end of the trial, irrespective of the outcome of the trial.

7.4 Trial duration

7.4.1 For an individual subject

The on-study estimated total duration of the study, from the time the informed consent document is signed until the last visit or the last scheduled procedures is up to 60 week for phase A and up to 3 years for phase B.

7.4.2 For the whole trial

We estimate to recruit subjects for a period of 56 months, last subject last visit (LSLV) will be reached 51 months later. The total duration of the study will thus be 107 months.

8 Trial Population

8.1 Number of subjects and planned recruitment rate

In total it is expected to recruit 110 patients, of which 90 patients will be randomized in this trial and reach the primary endpoint timepoint (taking into account screen failures and drop outs) They will be recruited in rheumatology departments of different hospitals. At the UZ Ghent, the UZ Leuven and ZNA Jan Palfijn sites synovial biopsy sampling units are operational. The inclusion of patients is competitive, meaning that there are no minimum or maximum quota for inclusions per center.

8.2 Inclusion and exclusion criteria

8.2.1 Inclusion criteria

8.2.1.1 SPARTACUS Phase A: “Remission-Induction Phase”

A subject will be eligible for study participation if all of the following criteria are met:

- Subjects must be able and willing to provide written informed consent and comply with the requirements of this study protocol.
- Subjects must be between 18 and 65 years of age.
- Subjects must have been diagnosed with peripheral spondyloarthritis by the treating rheumatologist.
- Subjects must meet the ASAS classification criteria for peripheral spondyloarthritis (see addendum 1): subjects must have current arthritis (asymmetric or predominantly in the lower limbs) or current enthesitis (except for enthesitis only along the spine, sacroiliac joints and/or chest wall) or current dactylitis plus at least 1 of the following SpA features:
 - Anterior uveitis confirmed by an ophthalmologist (past or present)
 - Crohn's disease or ulcerative colitis diagnosed by a gastroenterologist (past or present).
 - Evidence of preceding infection (acute diarrhea or non-gonococcal urethritis or cervicitis 1 month before arthritis).
 - Psoriasis diagnosed by a dermatologist (past or present).
 - HLA B27 positivity
 - Sacroiliitis by imaging defined as bilateral grade 2–4 or unilateral grade 3–4 sacroiliitis on plain radiographs, according to the modified New York criteria or

active sacroiliitis on MRI according to the ASAS consensus definition (ref of addendum).

- Subjects must have had onset of peripheral SpA symptoms ≤12 months prior to the screening visit.
- Subjects must have active disease at screening defined by Patient Global Assessment of Disease Activity Numerical Rating Scale (NRS) ≥ 4 and Patient Global Assessment of Pain NRS ≥ 4. At the baseline visit patients will be clinically evaluated to exclude spontaneous clinical remission.
- In subjects with concurrent axial SpA symptoms, the peripheral SpA symptoms must be the predominant symptoms at study entry based on the Investigator's clinical judgment.
- Subjects must have a negative PPD test (or equivalent) and chest radiography (anteroposterior and lateral view) at screening. If the subject has a positive PPD test (or equivalent), has had a past ulcerative reaction following PPD placement and/or a chest radiography consistent with prior TB exposure, the subject must initiate, or have documented completion of a course of anti-TB therapy.
- Women of childbearing potential or men capable of fathering children must be using adequate birth control measures during the study and for 6 months after receiving the last administration of study agent (cfr. section 8.7).
- Subject is judged to be in good health as determined by the principal investigator based upon the results of medical history, physical examination, laboratory profile, and chest x-ray (CXR) performed during screening.
- Subjects must be able and willing to self-administer SC injections or have a qualified person available to administer SC injections.

8.2.1.2 SPARTACUS Phase B: “Drug-Free Remission Phase”

A subject will be eligible for phase B of the study if all of the following criteria are met:

- Subjects must have participated in SPARTACUS Phase A.
- Subjects must have reached a status of sustained clinical remission (defined as absence of clinical arthritis, enthesitis and dactylitis at 2 consecutive 'major' visits with an interval of 12 weeks).

8.2.2 Exclusion criteria

- Medical history of inflammatory arthritis of a different etiology than peripheral spondyloarthritis (e.g. rheumatoid arthritis, systemic lupus erythematosus, gout, ...).
- Prior adequate treatment with methotrexate and/or sulphasalazine.
- Prior exposure to any biologic therapy with a potential therapeutic impact on SpA.
- Treatment with any investigational drug of chemical or biological nature within a minimum of 30 days or 5 half-lives of the drug (whichever is longer) prior to the Baseline Visit.
- Subject is taking or has taken prohibited medications as outlined in Table 1 without meeting the mandatory washout period(s) relative to the baseline visit.
- Infection(s) requiring treatment with intravenous (iv) anti-infective agents within 30 days prior to the Baseline visit or oral anti-infectives within 14 days prior to the baseline Visit.

- Have a known hypersensitivity to human immunoglobulin proteins or other components of golimumab.
- History of central nervous system (CNS) demyelinating disease or neurologic symptoms suggestive of CNS demyelinating disease.
- History of listeriosis, histoplasmosis, chronic or active Hepatitis B infection, Hepatitis C infection, human immunodeficiency virus (HIV) infection, immunodeficiency syndrome, chronic recurring infections or active TB.
- (History of) chronic heart failure (CHF), including medically controlled, asymptomatic CHF.
- History of malignancy (including lymphoma and leukemia) other than a successfully treated non-metastatic cutaneous squamous cell or basal cell carcinoma or localized carcinoma in situ of the cervix.
- Have received any live virus or bacterial vaccination within 3 months prior to the first administration of study agent; patients who are expected to receive such vaccinations during the trial, or within 3 months after the last administration of study agent.
- Positive serum pregnancy test at screening.
- Female subjects who are breast-feeding.
- Clinically significant abnormal screening laboratory results as evaluated by the Investigator.
- Positive anti-cyclic citrullinated peptide (anti-CCP) antibody at screening if the titers are crossing 3 times the upper limit of normal.
- Subject is considered by the investigator, for any reason, to be an unsuitable candidate for the study.
- Subject with current symptoms of fibromyalgia that would confound evaluation of the patient.

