11.4 Study specific Procedures and Interventions

11.4.1 ‘SPARTACUS Phase A’

Phase A – Visit 1A: CLINICAL SCREENING (week -6 to -4 days)

- Informed consent.
- Check fulfilment of in- and exclusion criteria.
- Demographic data, symptom duration, medical history, incl. past anti-rheumatic treatment, smoking/alcohol status, and family history.
- Current medication (dose and duration).

- Latent Tuberculosis (TB) screening: chest X-ray (if not performed within the last 3 months), TB test (Mantoux PPD-test or Quantiferon), TB questionnaire (see Addendum 4).
- Patient reported outcomes:
 - Patient global assessment of disease activity (0-10 numerical rating scale).
 - Patient global assessment of pain (0-10 numerical rating scale).
- Physical examination.
- Vital signs (blood pressure, heart frequency).
- Weight, length.
- Rheumatological examination (see Addendum 5):
 - 78-Tender and 76-swollen joint count.
 - Dactylitis assessment.
 - Enthesitis assessment (SPARCC (SPondyloArthritis Research Consortium of Canada) Enthesitis Index).
 - Physician global assessment of disease activity (0-10 numerical rating scale).
- Laboratory investigation:
 - Diagnosis: HLA B27 (if not known), anti-CCP antibodies (if not determined within the last 12 months).
 - Screening: peripheral blood count, serum creatinine, uric acid, liver function tests (ALT, gamma-GT, Alkaline Phosphatase, LDH), Creatine Kinase. (laboratory evaluations considered “standard-of-care” daily practice for SpA patients treated with csDMARDs and TNFi). (the results of tests performed within the last month are allowed).
 - Serum pregnancy test.
 - Screening for Hepatitis B, Hepatitis C, HIV and CMV IgG. (if not determined within the last 3 months).
 - Disease activity: inflammatory parameters: erythrocyte sedimentation rate (ESR), C-reactive protein (CRP).

Phase A – Visit 1B: SYNOVIAL BIOPSY SCREENING (week -6 to -4 days)

Performed in one of the synovial biopsy sampling units

- Ultrasound evaluation of clinically swollen joints identified at visit 1A.
- Ultrasound-guided synovial tissue sampling of a representative swollen joint (see Addendum 6 for list of joints that can be sampled). In case of multiple small joint involvement, a joint with a score of 2 or more on Grey Scale/Power Doppler ultrasound assessment will be chosen to sample.
- Laboratory investigation: Research samples (4 x 8ml blood-CPT (Cell Preparation Tube) and 10ml serum)
- Check fulfilment of in- and exclusion criteria.

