- Post biopsy questionnaire (see Addendum 9)

Phase A – Visit 2: BASELINE (week 0)

- Check fulfilment of in- and exclusion criteria.
- Current medication (dose and duration).
- Patient reported outcomes (see Addendum 7):

- Patient global assessment of disease activity (0-10 numerical rating scale).
- Patient global assessment of pain (0-10 numerical rating scale).
- Bath Ankylosing Spondylitis Disease Activity Index (BASDAI).
- Bath Ankylosing Spondylitis Functional Index (BASFI).
- Health Assessment Questionnaire (for SpA) (HAQ(-SpA)).
- Assessment of SpondyloArthritis international Society (ASAS) Health Index (ASAS-HI).
- “Health Economic Evaluation”: EuroQoL 5 dimensions, co-morbidity Index (SCQ) and healthcare utilization and productivity (in the past 6 months), level of education
- Targeted physical examination.
- Follow-up upon the synovial biopsy if performed
- Rheumatological examination (see Addendum 5):
 - 78-Tender and 76-swollen joint count.
 - Dactylitis assessment.
 - Enthesitis assessment (SPARCC Enthesitis Index).
 - Bath Ankylosing Spondylitis Metrology Index (BASMI), including tragus-to-wall distance, lumbar flexion (Schöber index), lumbar lateroflexion, cervical rotation and intermalleolar distance; chest expansion.
 - Psoriasis skin evaluation (if applicable).
- Laboratory investigation:
 - Research samples (if not taken at Visit 1B 4 x 8ml blood-CPT + 10ml serum if treated in a synovial biopsy sampling unit)
- Assessment of adverse events after start of blinded study medication.
- Dispensation of study drug and treatment schedule education/diary:
 - Administration of Golimumab/Placebo injection at study site.
 - Dispensation of Placebo/Methotrexate capsules for weekly intake at home.

Phase A – Visit 3: WEEK 4 (+/- 1 week)

- Assessment of adverse events.
- Current medication (dose and duration).
- Study drug accountability.
- Patient reported outcomes (see Addendum 7):
 - Patient global assessment of disease activity (0-10 numerical rating scale).
 - Patient global assessment of pain (0-10 numerical rating scale).
 - Bath Ankylosing Spondylitis Disease Activity Index (BASDAI).
- Targeted physical examination.
- Rheumatological examination (see Addendum 5):
 - 78-Tender and 76-swollen joint count.
 - Dactylitis assessment.
 - Enthesitis assessment (SPARCC Enthesitis Index).
- Laboratory investigation:
 - Disease activity: ESR, CRP.
 - Safety: peripheral blood count, serum creatinine, liver function tests (ALT).

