	scr	Biopt	W0	W4	W8	W12	W16	W20	W24	W28	W36	W48	W60	
Informed Consent	X													
Inclusion/Exclusion crit	X	X	X											
synovial biopsy & Ultrasound		X												
Anamnesis ^a	X													
Current Medication	X		X	X	X	X	X	X	X	X	X	X	X	X
Adverse Events			X	X	X	X	X	X	X	X	X	X	X	X
Latent TB screening ^b	X					X			X		X	X	X	
Patient disease activity & pain NRS	X		X	X	X	X	X	X	X	X	X	X	X	X
BASDAI			X	X	X	X	X	X	X	X	X	X	X	X
BASFI, ASAS-HI, Health economic evaluations			X			X			X		X	X	X	
HAQ-SpA			X						X			X		
Post biopsy questionnaire		X												
(Targeted) Physical examination ^f	X		X	X	X	X	X	X	X	X	X	X	X	X
Vital Signs	X					X			X		X	X	X	
Length (only at screening), weight	X					X			X		X	X	X	
Smoking/alcohol status	X					X			X		X	X	X	
76SJC/78TJC, dactylitis, enthesitis (SPARCC)	X		X	X	X	X	X	X	X	X	X	X	X	X
BASMI, chest expansion, Psoriasis assessment			X			X			X		X	X	X	X
Physician global NRS	X					X			X		X	X	X	
HLA B27 ^c , anti-CCP AB ^d , HBV ⁱ , HCV ⁱ , HIV ⁱ , CMV IgG ⁱ	X													
Safety Lab tests ^e	X ^e			X	X	X	X	X	X	X	X	X	X	X
ESR, CRP	X		X	X	X	X	X	X	X	X	X	X	X	X
Serum Pregnancy Testing	X													
Research samples ^g		X	X ^h			X			X					
PASSI						X					X	X		
Assessment of clinical remission status						X			X		X	X	X	
Study drug admin/dispensation			X	X	X	X	X	X	X	X	X	X	X	
Study drug accountability				X	X	X	X	X	X	X	X	X	X	

^a Demographic data, symptom duration, medical history, past anti-rheumatic treatment, family history

^b v1A: chest X-ray (if not performed within the last 3 months), TB test (Mantoux PPD-test or Quantiferon), TB questionnaire; other visits: only TB questionnaire

^c If not known

^d if not determined within the last 12 months

^e At v1A (for visit 1A: results of tests performed within the last month are allowed), week 24, week 36, week 48, week 60: peripheral blood count, serum creatinine, uric acid, liver function tests (ALT, GGT, AP, LDH), CK

At week 4, week 12, week 28: peripheral blood count, serum creatinine, ALT

At week 8, week 16, week 20: at the discretion of the treating rheumatologist

At the unscheduled visit: at the discretion of the treating rheumatologist

^f Full physical exam at screening, targeted physical exam at the other visits

^g 4 x 8ml blood-CPT (the synovial biopsy sampling units will also collect 10ml serum; at week 12: only 10ml serum; ZNA Jan Palfijn will only collect serum at BL)

^h Only if no samples taken at visit 1B

ⁱ if not determined within the last 3 months

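### The only scheduled pregnancy test is at Visit 1A, so the first blinded dose may be given on a negative result 4 to 42 days old

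*Protocol*

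**What the plan says.** The exclusion criterion in Protocol 8.2.2 is "Positive serum pregnancy test at screening". It names no later test.

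Section 11.4.1 heads Visit 1A "CLINICAL SCREENING (week -6 to -4 days" and lists "Serum pregnancy test" among its laboratory investigations. In the Phase A flowchart the row "Serum Pregnancy Testing" has a single mark, under V1A.

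Visit 2 is the baseline visit, week 0. Its list includes "Check fulfilment of in- and exclusion criteria" and then the first treatment: "Administration of Golimumab/Placebo injection at study site", together with a first supply of methotrexate or placebo capsules to take at home. The laboratory work in the Visit 2 text is research samples; the flowchart adds ESR and CRP. Neither shows a pregnancy test.

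On contraception, 8.2.1.1 says that women of childbearing potential "must be using adequate birth control measures during the study and for 6 months after receiving the last administration of study agent". Section 7.4.1 counts an individual's time on study "from the time the informed consent document is signed until the last visit".

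**The concern.** Pregnancy status can change between screening and first dose, yet the criterion is fixed to a screening result. Other changeable conditions in the same list are timed differently: investigational drugs, prohibited-medication washouts and recent infections are counted back from the baseline visit, and live vaccines from the first administration of study agent. Section 8.2.1.1 also asks for a clinical re-evaluation at baseline in case the disease has remitted on its own. Pregnancy has no such re-check.

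What is at stake is exposure of an unrecognised pregnancy to the first dose of blinded medication. The protocol itself treats such exposure as important: contraception continues for 6 months after the last dose, egg and sperm donation are barred for the same period (8.7), pregnancy is a listed reason to stop treatment (8.3.1), and pregnancies must be reported within 24 hours (15.2.2).

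**Working it through.** **1. Where pregnancy testing is scheduled**

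| Place in the protocol | Pregnancy test? |
|---|---|
| 11.4.1, Visit 1A | Yes, serum |
| 11.4.1, Visit 1B (biopsy screening) | None listed |
| 11.4.1, Visit 2 (week 0) | None listed |
| 11.4.1, Visits 3 to 12 and unscheduled visit | None listed |
| Phase A flowchart | One mark, at V1A |
| Flowchart footnote on safety laboratory tests | Not part of any panel |
| Phase B schedule | None |

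Scheduled tests from Visit 1B onward: 0.

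**2. Age of the result at first dose**

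Inputs: the Visit 1A window in 11.4.1 (week -6 to day -4) and first dosing at Visit 2 (week 0).

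- Oldest result: 6 weeks x 7 days = 42 days.
- Newest result: 4 days.

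At Visit 1A, results up to a month old are accepted for the routine safety panel (blood count, creatinine, liver tests and so on). That allowance is not attached to the pregnancy test, so the upper limit stays at 42 days.

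**3. Whether another rule closes the interval**

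- *Contraception (8.2.1.1, 8.7).* Because time on study runs from consent (7.4.1), the requirement plausibly covers the whole gap. It lowers the chance of conception but does not detect one. The accepted methods include daily pills and abstinence, which depend on adherence.
- *Repeated eligibility checks (Visits 1A, 1B and 2).* The pregnancy criterion they check refers to the Visit 1A result, so the check at Visit 2 reads the same result again.
- *Investigator discretion.* A known pregnancy can be handled under the unsuitable-candidate criterion in 8.2.2, or by stopping treatment under 8.3.1. Both require the pregnancy to be known.

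**4. What a positive test at Visit 2 would put at risk**

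Under 11.3.1, randomisation is approved from the screening data and the kit is then sent to the site. The kit holds 6 scheduled syringes + 1 spare = 7 golimumab/placebo syringes assembled for that patient. Methotrexate and placebo bottles are not tied to a patient and are allocated per visit, so they are not lost.

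**The case against.** The strongest case against raising this is that nothing is misstated. Criterion, visit list and flowchart agree, and no section sets a maximum age for the test or promises one before dosing. The chosen safeguard is contraception, limited to hormonal methods, intrauterine devices, abstinence or sterilisation, and eligibility is checked three times. The side-effect sections (9.2.8, 9.5.8) do not mention fetal harm. No pregnancy test is scheduled during treatment either, which can last to week 60; singling out the weeks before dosing may look arbitrary. The amendment needs approval, and recruitment may be well advanced.

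Much of this stands. A reader might infer that the protocol contradicts itself; it does not. A reader might infer that the investigator cannot have a fresh result at Visit 2; in fact none is scheduled, and nothing prevents an investigator from testing. A reader might take 42 days as typical; it is the outer limit, and actual intervals are not reported.

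Two parts do not stand. Contraception and repeated criterion checks reduce risk, but neither can show an unrecognised conception. And the time before first dose is not an arbitrary choice: it is the last point at which exposure can be avoided altogether, at a visit that already includes an eligibility decision. Whether testing during treatment is also wanted is a separate question, on which this point takes no position.

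**Conclusion.** The point holds as a modest patient-safety improvement. The schedule allows the first golimumab/placebo and methotrexate/placebo treatment on a negative pregnancy result 4 to 42 days old, and no later test is scheduled to show a conception in between.

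The number of events cannot be estimated. The documents give neither the number of women of childbearing potential still to be dosed nor the actual screening intervals. Few events are expected because contraception is required; that expectation assumes that the requirement applies from consent and is followed.

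A reader might infer that pregnant women are likely to be dosed, or that the trial result is threatened. The documents support neither. No sample-size, power or primary-analysis figure rests on this test.

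**What to change.** For women of childbearing potential not yet dosed, require a negative urine pregnancy test at Visit 2 before the first injection and capsules:

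1. In 8.2.2, change the criterion to: *Positive pregnancy test at screening or at baseline before first dose.*
2. Add the urine test to the Visit 2 list in 11.4.1, ahead of dispensing.
3. Mark V2 in the pregnancy row of the Phase A flowchart, and reword the row so that it is not limited to serum.

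Leave 8.3.2 as it is. It bars replacement only after a first dose, so this fix needs no new replacement rule, and adding one would affect the randomised set.

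Cost: one urine test per woman concerned, at an existing visit and without a blood draw; regulatory approval if the change is substantial (17.3.2), and roll-out to sites. Because randomisation precedes Visit 2, a positive test would occasionally leave a randomised but undosed patient and possibly a wasted kit of 7 syringes. Testing just before randomisation is approved would avoid most of that waste, but would leave the time for kit shipment uncovered. The wording change can go into the next amendment.

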8.2.3 Justification of in- and exclusion criteria

Not applicable

8.3 Withdrawal and replacement of subjects

8.3.1 Withdrawal of subjects

Subjects are free to withdraw from participation in the trial at any time. A subject must be discontinued from the trial if *the subject* withdraws consent. The reason why a subject withdraws consent, if given, must be recorded in detail in the electronic Case Report Form (eCRF) and in the subject's medical records. The already gathered subject data should remain in the trial database.

However, subjects can choose to discontinue trial treatment or interventions, but remain in the trial for other assessments or data collection, if applicable. The reasons for a subject to withdraw from trial treatment, if given, must be recorded in detail in the electronic Case Report Form (eCRF) and in the subject's medical records. The subject data should be collected in the eCRF.

An investigator may discontinue trial treatment for a subject for the following reasons:

- Pregnancy;

- Significant trial intervention non-compliance;
- If any clinical adverse event (AE), laboratory abnormality, or other medical condition or situation occurs such that continued participation in the trial would not be in the best interest of the subject;
- Disease progression which requires discontinuation of the trial intervention;
- If the subject meets an exclusion criterion (either newly developed or not previously recognized) that precludes further trial participation;
- Subject unable to receive study intervention for a duration of at least 3 months

The reasons for withdrawing a subject from study treatment must be recorded in detail in the electronic Case Report Form (eCRF) and in the subject's medical records. However, even if trial treatment is discontinued, the subject will remain in the trial and other assessments or data collection should be done, if applicable. The subject data should be collected in the eCRF.

A subject will be considered lost to follow-up if he or she fails to return for 2 consecutive scheduled visits and is unable to be contacted by the trial site staff.

The following actions must be taken if a subject fails to return for a required trial visit:

- The site will attempt to contact the subject and reschedule the missed visit as soon as possible and counsel the subject on the importance of maintaining the assigned visit schedule and ascertain if the subject wishes to and/or should continue in the trial;
- Before a subject is deemed lost to follow-up, the investigator or designee will make every effort to regain contact with the subject (when possible, three telephone calls and if necessary a certified letter to the subject's last known mailing address or local equivalent methods). These contact attempts should be documented in the subject's medical record or study file;
- Should the subject continue to be unreachable, he or she will be considered to have withdrawn from the trial with a primary reason of lost to follow-up.

